4.1.2. Exclusion Criteria

Patients meeting any of the following criteria will not be included in the study:

[figure not shown]
Enrollment in an interventional clinical trial for A/MBC during the study observation period.

4.2. Subgroups

Summaries of study outcomes may be repeated focusing alternatively on but not limited to the following subgroups of interest—sample size permitting—which will be defined on the basis of:

- Age (years): ≤ 50 , 51-64, 65-74, ≥ 75 ;
- Gender, if number of males is low then we can restrict results to females;
- Race: White, Black, Other;
- Disease stage at initial diagnosis: I or II, III, IV;
- ECOG performance status: 0, 1 or 2, ≥ 3 ;
- Site of metastasis: Visceral, Non-visceral, Bone only;
- Number of metastatic sites: 1, 2, ≥ 3 ;

PFIZER CONFIDENTIAL

- Menopausal status: premenopausal, perimenopausal, Postmenopausal, undocumented;
- Hormone therapy prior to A/MBC diagnosis: yes, no;
- Chemotherapy prior to A/MBC diagnosis: yes, no;
- Surgery prior to A/MBC diagnosis: yes, no;
- Radiation therapy prior to A/MBC diagnosis: yes, no;
- Disease free interval: ≤ 12 months, > 12 months;
- Starting dose: by starting dose levels for Palbociclib, CCI

5. ENDPOINTS AND COVARIATES

- Index date:** Date of A/MBC diagnosis.
- Observation period:** February 3, 2015 through the data cutoff date (end of data curation). Since data curation will start in November 2019, this allows patients to have a potential follow-up of at least 6 months.
- Follow-up:** Patients will be followed from the index date to the data cutoff date, or death, whichever comes first.

5.1. DEMOGRAPHIC AND CLINICAL CHARACTERISTICS

Variable	Operational definition
Demographic characteristics	
Age	Age at A/MBC diagnosis, years
Age category	≤ 50 , 51-64, 65 –74, ≥ 75 years
Sex	Female or Male
Race	White, Black, Asian, Other, Unknown
Region of residence	Based on state where the patient resides: Northeast, Midwest, South, West
Insurance status	Private only, public only, public and private, or neither reported at index date and reported at initiation of the earliest endocrine-based therapy after the index date.
Clinical characteristics	
Menopausal status	(Pre, Peri, Post, UD) nearest in time to the date of, but before, index date.
Type of MBC	De novo MBC (newly diagnosed): Stage 4 at initial BC diagnosis Recurrent MBC: Stages 0-3 at initial BC diagnosis
Modalities of treatment received at any point prior to A/MBC diagnosis	Surgery (yes/no), Radiation (yes/no), Chemotherapy (yes/no), Hormone therapy (yes/no)

PFIZER CONFIDENTIAL

ECOG performance score	ECOG performance at index date (\pm 60 days), 0, 1,2,3,4,5, or missing. Where available, Karnofsky performance status will be converted to the corresponding ECOG score.
Disease stage at initial BC diagnosis	Stage I, II, III, IV, unknown/ undocumented
Disease stage at index date (date of A/MBC diagnosis)	IIIB, IIIC, or IV
Time from initial BC diagnosis to first MBC diagnosis	Months from the date of initial BC diagnosis to the date of metastatic diagnosis.
Disease free interval	The number of months between completion of adjuvant therapy and diagnosis of A/MBC.
Sites of distant metastasis at index date	Bone; Chest Wall; Contralateral Breast; Distant Lymph node(s); Liver; Lung; Peritoneum; Pleural nodules; Malignant pleural effusion; Skin; Brain; Undocumented; Other Specified. All sites will be reported as (yes/no).
Visceral metastasis at index date	Metastasis at one or more of the following sites: liver, pancreas, intestines, lung, heart, malignant pleural effusion, peritoneum, pleura. Other metastasis sites, including bone or non-visceral metastasis, may be present.
Non-visceral metastasis at index date	Metastasis at one or more of the following sites: bone, brain, skin, chest wall, contralateral breast, or distant lymph nodes.
Bone-only metastasis at index date	Bone metastasis, with no metastasis at any other identified site
Disease histology nearest in time to index date	Adenoid cystic; Cribriform; Ductal; Inflammatory; Intraductal; Lobular; Medullary with lymphoid stroma; Medullary, NOS; Mucinous; Paget's disease and infiltrating; Paget's disease and intraductal; Papillary; Secretory; Squamous cell; Tubular; Undifferentiated; Undocumented, Other, specify.

PFIZER CONFIDENTIAL

Endocrine sensitivity	
Sensitive/Resistant/Refractory
 
Endocrine sensitive vs. resistant vs. refractory based on adjuvant endocrine therapy experience. Endocrine sensitive: ≥ 24 months without recurrence / progression after completion of endocrine therapy in the adjuvant setting; Endocrine resistant: recurrence / progression after completion of endocrine therapy, and within 24 months of completion of endocrine therapy; Endocrine refractory: recurrence / progression while on endocrine therapy in the adjuvant setting, defined as occurring while on or within < 30 days after discontinuation of endocrine therapy. The 30 day window allows that endocrine therapy may be discontinued because of a perceived progression before that progression is actually documented.

Type of endocrine resistance	
Primary/Secondary
 
Primary endocrine resistance defined as a relapse while on the first 2 years of adjuvant endocrine therapy or disease progression within the first 6 months of first-line endocrine therapy for A/MBC, while on endocrine therapy.
 
Secondary (acquired) endocrine resistance defined as a relapse while on adjuvant endocrine therapy but after the first 2 years or a relapse within 12 months of completing adjuvant endocrine therapy, or disease progression ≥ 6 months after initiating endocrine therapy for A/MBC, while on endocrine therapy.

Comorbidities present at index date	
Myocardial infarction, congestive heart failure, peripheral vascular disease, cerebrovascular accident, hemiplegia, chronic obstructive pulmonary disease, ulcer disease, diabetes, renal disease, connective tissue disease such as rheumatoid arthritis or lupus, Alzheimer's or other dementia, cirrhosis or other serious liver disease, leukemia, lymphoma, metastatic solid tumor (other than breast cancer), and HIV/AIDS, hypertension and hyperlipidemia.
 
Indicated as present or not indicated as present at index date.

PFIZER CONFIDENTIAL

Modified Charlson comorbidity index (CCI)	Weighted index of comorbid disease conditions (not including breast cancer) as specified by the Charlson Comorbidity Index.
---	---

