4.1.1. Inclusion criteria

Patients must meet all of the following inclusion criteria to be eligible for inclusion in the study:

1. *Female or male sex.*
2. *Diagnosis (confirmed by clinical review) of A/MBC, defined as breast cancer at stage IIIB, stage IIIC, stage IV or identified as having distant metastasis.*
3. *Age ≥ 18 years at A/MBC diagnosis.*
4. *Initiated a CDK4/6i in combination with an AI as initial endocrine-based therapy after A/MBC diagnosis on or after 2/3/2015 and before 4/1/2019.*
 - *Note that the date of the start of the inclusion period reflects the month that the first CDK4/6i (ie, Palbociclib) received U.S. FDA approval.*
5. *Evidence of ER or PR positive disease, or absence of any indication of ER and PR negative disease closest to A/MBC diagnosis (ie, patients are eligible without affirmative indication of ER/PR+ status as long as ER/PR- indication is not present).*
6. *Evidence of HER2 negative disease, or absence of any indication of HER2 positive disease closest to A/MBC diagnosis (ie, patients are eligible without affirmative indication of HER2- status as long as HER2+ indication is not present).*

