7.2.2. Summary of Analyses of Efficacy/Effectiveness Outcomes

Outcome	Analysis Set(s)	Supports Protocol Objective Number	Missing Data
Real-world progression-free survival	All Eligible Patients Palbociclib + AI Patients CCI	2, 3	Excluded
Overall survival	All Eligible Patients Palbociclib + AI Patients CCI	2, 3	Excluded
Real-world tumor response	All Eligible Patients Palbociclib + AI Patients CCI	2, 3	Excluded
Response rate	All Eligible Patients Palbociclib + AI Patients CCI	2, 3	Excluded
Time to first positive response	All Eligible Patients Palbociclib + AI Patients CCI	2, 3	Excluded
Duration of response	All Eligible Patients Palbociclib + AI Patients CCI	2, 3	Excluded

PFIZER CONFIDENTIAL

Duration of initial endocrine based treatment	All Eligible Patients Palbociclib + AI Patients CCI [REDACTED]	1b	Excluded
Duration of all treatment	All Eligible Patients Palbociclib + AI Patients CCI [REDACTED]	1b	Excluded
Duration of follow-up	All Eligible Patients Palbociclib + AI Patients CCI [REDACTED]	1b	Excluded

PFIZER CONFIDENTIAL

8. REFERENCES**9. APPENDICES****9.1. APPENDIX 1: Table and Figure shells****Table 1a. Summary of Baseline Demographics – All Eligible Patients**

	All Eligible Patients (N=)
Age at A/MBC Diagnosis (years)	
Mean/SD	
N/Missing Values	
Min/Max	
First Quartile/Third Quartile	
Median/IQR	
Age Distribution (years), n (%)	
≤50	
51-64	
65 –74	
≥75	
Missing	
Sex, n (%)	
Female	
Male	
Missing	
Race, n (%)	
White	
Black	
Asian	
Other	
Unknown	
Missing	
Insurance Status, n (%)	
Private only	
Public only	
Public and Private	
Neither Public nor Private	
Missing	
Region of residence, n (%)	
Northeast	
Midwest	
South	
West	
Missing	

PFIZER CONFIDENTIAL

Table 1b. Summary of Baseline Demographics – Palbociclib + AI Patients

Repeat Table 1a for patients receiving Palbociclib with AI as initial endocrine-based therapy.

CCI

CCI	[REDACTED]
	[REDACTED]
	[REDACTED]
	[REDACTED]

Table 2a. Summary of Clinical Characteristics – All Eligible Patients

	All Eligible Patients (N=)
Number of Female Patients, n	
Menopausal Status, n (%) ^a	
Premenopausal	
Perimenopausal	
Postmenopausal	
Undocumented	
Missing	
Disease Stage at Initial Diagnosis, n (%)	
I	
II	
III	
IV	
Unknown/Undocumented	
Missing	
Disease Stage at Index Date, n (%)	
IIIB	
IIIC	
IV	
Missing	
Type of MBC	
De novo (Stage 4 at initial diagnosis)	
Recurrent (Stages 0-3 at initial diagnosis)	
Missing	
Time from Initial Diagnosis to First A/MBC Diagnosis	
Mean/SD	
N/Missing Values	
Min/Max	

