^d Visceral: metastasis at one or more of the following sites: liver, pancreas, intestines, lung, heart, malignant pleural effusion, peritoneum, pleura. Other metastasis sites, including bone or non-visceral metastasis, may be present.

^e Non-visceral: metastasis at one or more of the following sites: bone, brain, skin, chest wall, contralateral breast, or distant lymph nodes.

^f Bone only: Bone metastasis, with no metastasis at any other identified site.

Table 2b. Summary of Clinical Characteristics – Palbociclib + AI Patients

Repeat Table 2a for patients receiving Palbociclib with AI as initial endocrine-based therapy.

CCI

Table 3a. Summary of Treatment Regimen Duration – All Eligible Patients

		Treatment Regimen Duration (months)				
		n	%	Mean	SD	Median
Line 1	Regimenx	XXX	XXX	XXX	XXX	XXX
	Regimeny	XXX	XXX	XXX	XXX	XXX
	Regimenz	XXX	XXX	XXX	XXX	XXX
	...	XXX	XXX	XXX	XXX	XXX
Line 2	Regimenx	XXX	XXX	XXX	XXX	XXX
	Regimeny	XXX	XXX	XXX	XXX	XXX
	Regimenz	XXX	XXX	XXX	XXX	XXX
	...	XXX	XXX	XXX	XXX	XXX
Line 3	Regimenx	XXX	XXX	XXX	XXX	XXX
	Regimeny	XXX	XXX	XXX	XXX	XXX
	Regimenz	XXX	XXX	XXX	XXX	XXX
	...	XXX	XXX	XXX	XXX	XXX

Lines of therapy are progression-based and are restricted to the first 3 lines.

Table 3b. Summary of Treatment Regimen Duration – Palbociclib + AI Patients

Repeat Table 3a for patients receiving Palbociclib with AI as initial endocrine-based therapy.

[figure not shown]
CCI

Table 4a. Summary of Treatment Sequencing Duration – All Eligible Patients

	Treatment Sequence	Duration (month)				
		n	%	Mean	SD	Median
One line	Line 1 Regimenx	XXX	XXX	XXX	XXX	XXX
	Line 1 Regimeny	XXX	XXX	XXX	XXX	XXX
	Line 1 Regimenz	XXX	XXX	XXX	XXX	XXX
	...	XXX	XXX	XXX	XXX	XXX
Two lines	Line 1 Regimen ==> Line 2 Regimen	XXX	XXX	XXX	XXX	XXX
	Line 1 Regimen ==> Line 2 Regimen	XXX	XXX	XXX	XXX	XXX
	Line 1 Regimen ==> Line 2 Regimen	XXX	XXX	XXX	XXX	XXX
	...	XXX	XXX	XXX	XXX	XXX

PFIZER CONFIDENTIAL

Three lines	Line 1 Regimen ==> Line 2 Regimen ==> Line 3 Regimen	xxx	xxx	xxx	xxx	xxx
	Line 1 Regimen ==> Line 2 Regimen ==> Line 3 Regimen	xxx	xxx	xxx	xxx	xxx
	Line 1 Regimen ==> Line 2 Regimen ==> Line 3 Regimen	xxx	xxx	xxx	xxx	xxx
	...	xxx	xxx	xxx	xxx	xxx

Lines of therapy are progression-based and are restricted to the first 3 lines.

Table 4b. Summary of Treatment Sequencing Duration – Palbociclib + AI Patients

Repeat Table 4a for patients receiving Palbociclib with AI as initial endocrine-based therapy.

CCI

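### Time from initial to metastatic diagnosis is pooled over de novo and recurrent patients, so its summary mixes recurrence timing with the de novo share; the end date also differs between SAP 5.1 and Table 2a

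*SAP*

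**What the plan says.** SAP 5.1 defines the interval from initial breast cancer diagnosis to first MBC diagnosis as "Months from the date of initial BC diagnosis to the date of metastatic diagnosis". It gives no restriction by type of disease and no rule for patients who were already metastatic when first diagnosed.

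The same section defines type of MBC: "De novo MBC (newly diagnosed): Stage 4 at initial BC diagnosis Recurrent MBC: Stages 0-3 at initial BC diagnosis". Both types are eligible. SAP 4.1.1 admits A/MBC "defined as breast cancer at stage IIIB, stage IIIC, stage IV or identified as having distant metastasis", and nothing in 4.1.2 excludes Stage 4 at first diagnosis.

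In SAP Appendix 1, Table 2a has one block for the interval (mean, SD, N and missing, range, quartiles, median, IQR) in a single All Eligible Patients column. The row label is "Time from Initial Diagnosis to First A/MBC Diagnosis", so the end point there is A/MBC diagnosis, not metastatic diagnosis. De novo and recurrent patients are counted in the row just above, but the interval is not split by them. Table 2b follows the same layout: "Repeat Table 2a for patients receiving Palbociclib with AI as initial endocrine-based therapy".

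**The concern.** For a patient who is Stage 4 at initial diagnosis, the initial and metastatic diagnoses are the same clinical event. The interval is about zero because of how the group is defined, and it says nothing about how long disease took to return. Pooling these values with the intervals of recurrent patients gives a summary that depends on two things at once: the timing in recurrent patients and the proportion who were de novo. If the de novo share rises while recurrence timing stays the same, the reported mean and median fall.

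At stake is the readability of one baseline row. A reader who takes the median as the usual time to metastatic disease would get a figure that is too low for recurrent patients. A difference between this study and another could come from case mix alone.

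**Working it through.** **Inputs.** The documents state no figure for this variable, so there is nothing to reproduce. The definitions and table layout come from SAP 5.1 and Tables 2a/2b. The de novo share d and the distribution of the interval in recurrent patients are not given. I assume d from 5% to 50%. For the recurrent interval I assume a lognormal with log-SD 0.5, 0.8 or 1.0, or an exponential. De novo values are set at zero; recorded dates may differ by days or weeks, which does not matter here.

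**Formulas.** With a share d at zero and the rest following the recurrent distribution:

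- pooled mean = (1 − d) × recurrent mean
- pooled median = recurrent quantile at level (0.5 − d)/(1 − d), and 0 if d ≥ 0.5
- pooled first quartile = recurrent quantile at level (0.25 − d)/(1 − d), and 0 if d ≥ 0.25

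For any d > 0 the level (0.5 − d)/(1 − d) is below 0.5, so the direction does not depend on the assumptions. For example, at d = 0.30 the level is 0.20/0.70 = 0.286.

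**Pooled value as a fraction of the recurrent value.** The median range runs over the four assumed distributions.

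| d | Recurrent percentile shown as the median | Mean | Median | First quartile |
|---|---|---|---|---|
| 5% | 47.4 | 0.95 | 0.93–0.97 | above 0 |
| 10% | 44.4 | 0.90 | 0.85–0.93 | above 0 |
| 20% | 37.5 | 0.80 | 0.68–0.85 | above 0 |
| 30% | 28.6 | 0.70 | 0.49–0.75 | 0 |
| 40% | 16.7 | 0.60 | 0.26–0.62 | 0 |
| 50% | 0 | 0.50 | 0 | 0 |

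**Illustration in months.** Assume a recurrent median of 60 months and log-SD 0.8. The recurrent mean is 60 × exp(0.8²/2) = 82.6.

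- d = 10%: mean 0.90 × 82.6 = 74.4; median 0.894 × 60 = 53.6
- d = 20%: mean 66.1; median 0.775 × 60 = 46.5
- d = 30%: mean 57.8; median 0.636 × 60 = 38.2
- d = 40%: mean 49.6; median 0.461 × 60 = 27.7

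**The two end dates.** A/MBC includes stages IIIB and IIIC, while recurrent MBC covers Stages 0–3 at initial diagnosis.

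- Under the Table 2a label, a patient first diagnosed at IIIB or IIIC reaches A/MBC at that diagnosis. That patient scores about zero, yet is classed as recurrent.
- Under the SAP 5.1 text, the same patient has a value only if metastatic disease is later diagnosed.

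So restricting the row to recurrent patients would not remove all the structural zeros while the Table 2a label stands. Under that label the share at zero is d plus the share first diagnosed at IIIB/IIIC.

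**The case against.** The strongest reply is that the row is correct under its own label. It reports time from initial to metastatic (or A/MBC) diagnosis, and near zero is the true value for a Stage 4 presentation. That stands: the problem is interpretability, not a wrong calculation.

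A reader might infer that the row greatly understates time to recurrence. The documents do not support this. They do not label the row time to recurrence, and they give no de novo share. At 5–10% the effect is small.

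A reader might also take the row for a descriptor that Objective 1a names. It is not in the list in Protocol section 8 or SAP 2.2. The timing variable listed there is the disease free interval, which has its own row in Table 2a. That interval starts at completion of adjuvant therapy, so de novo patients add no zeros to it. It does not replace this row: its start date differs, and recurrent patients without adjuvant therapy have no value.

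Nor does pooling make the two cohorts impossible to compare. Palbociclib + AI is a subset of All Eligible, SAP 3.1 and 3.2 set no hypotheses or decision rules, and the de novo and recurrent counts stand beside the row. With exact zeros and complete data, the recurrent mean is the pooled mean divided by (1 − d). The recurrent SD can be back-calculated in the same way, since the recurrent mean square is (pooled variance + pooled mean²)/(1 − d). The recurrent median and quartiles cannot in general be recovered from the pooled row.

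Two provisions might seem to cure the pooling. SAP 4.2 says "Summaries of study outcomes may be repeated focusing alternatively on but not limited to the following subgroups of interest", and its list includes stage at initial diagnosis. But that is optional and concerns outcomes, not this baseline row. The missing-data rules in SAP 6 and 7.2 do not set de novo values to missing.

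**Conclusion.** The point holds as a minor one. The interval is pooled over de novo and recurrent patients, no split is planned, and for any de novo share above zero the pooled mean is below, and the pooled median at or below, the recurrent value. The size is not known from the documents. Under the assumed shares and distributions it is small at 5–10% and large from about 30%, where the pooled median is roughly half to three quarters of the recurrent median and the first quartile is zero. From 50% the median is zero whatever the recurrent distribution.

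The end-date mismatch between SAP 5.1 and Table 2a needs no assumption and has to be settled in the same edit.

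The effect is confined to one descriptive baseline row. A reader might infer that the effectiveness results are affected; they are not, because rwPFS, OS and rwTR do not use this variable.

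**What to change.** In SAP 5.1 and Tables 2a/2b:

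1. Report the interval by type of MBC. Give the main summary in recurrent MBC patients with that group's N, and show de novo patients as n (%).
2. Use one end date in both places. Metastatic diagnosis fits the variable's name in SAP 5.1. Protocol 9.3.2 already collects the date of Stage IV/metastatic diagnosis for patients who are IIIB or IIIC at the index date.
3. State that patients first diagnosed at IIIB/IIIC who never become metastatic have no value for this variable.
4. Count patients with unknown or undocumented initial stage separately, since they fit neither type.

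The dates and stages needed are already in the curated data, so the cost is a few lines of SAP wording and a change to the table shell. The downside is a smaller N for the row, which then excludes patients whose type is unknown even if both their dates are recorded.

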9.2. Setting

9.2.1. Inclusion Criteria

Patients must meet all of the following inclusion criteria to be eligible for inclusion in the study:

1. Female or male sex.

PFIZER CONFIDENTIAL

[REDACTED]

2. Diagnosis (confirmed by clinical review) of A/MBC, defined as breast cancer at stage IIIB, stage IIIC, stage IV or identified as having distant metastasis.
3. Age ≥ 18 years at A/MBC diagnosis.
4. Initiated a CDK4/6i in combination with an AI as initial endocrine-based therapy after A/MBC diagnosis on or after 2/3/2015 and before 4/1/2019.
 - Note that the date of the start of the inclusion period reflects the month that the first CDK4/6i (ie, Palbociclib) received U.S. FDA approval.
5. Evidence of ER or PR positive disease, or absence of any indication of ER and PR negative disease closest to A/MBC diagnosis (ie, patients are eligible without affirmative indication of ER/PR+ status as long as ER/PR- indication is not present).
6. Evidence of HER2 negative disease, or absence of any indication of HER2 positive disease closest to A/MBC diagnosis (ie, patients are eligible without affirmative indication of HER2- status as long as HER2+ indication is not present).

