**Table 11a. Duration of Response - All Eligible Patients**

	All Eligible Patients (N=)
Number of PD or Death, n (%)	
Number Censored, n (%)	
Kaplan-Meier Estimates of Time to Event (months)	
Median (95% CI)	

Table 11b. Duration of Response - Palbociclib + AI Patients

Repeat Table 11a for patients receiving Palbociclib with AI as initial endocrine-based therapy.

CCI

[figure not shown]
Figures

Kaplan-Meier curves for Palbociclib + AI initial endocrine therapy. Figures will contain the KM-estimated median survival and 95% confidence intervals in the legend.

Figure 1a: Real-world Progression-free Survival – All Eligible Patients

Figure 1b: Real-world Progression-free Survival – Palbociclib + AI Patients

CCI

Overall Survival – All Eligible Patients

Figure 2b: Overall Survival – Palbociclib + AI Patients

CCI

Figure 3a: Duration of Initial Endocrine-based Treatment – All Eligible Patients

Figure 3b: Duration of Initial Endocrine-based Treatment – Palbociclib + AI Patients

CCI

[figure not shown]
[figure not shown]

Figure 4a: Duration of All Treatment – All Eligible Patients

Figure 4b: Duration of All Treatment – Palbociclib + AI Patients

CCI

[figure not shown]

Figure 5a: Duration of Follow-up – All Eligible Patients

Figure 5b: Duration of Follow-up – Palbociclib + AI Patients

CCI

[figure not shown]

Figure 6a: Time to First Positive Response – All Eligible Patients

Figure 6b: Time to First Positive Response – Palbociclib + AI Patients

CCI

[figure not shown]
[figure not shown]

Figure 7a: Duration of Response – All Eligible Patients

Figure 7b: Duration of Response – Palbociclib + AI Patients

CCI

Additional figures will be generated for designated subgroup analyses.

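### Minor: the levels of the optional SAP 4.2 site-of-metastasis subgroup overlap, because Non-visceral excludes neither visceral nor bone-only disease

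*SAP*

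**What the plan says.** SAP 4.2 introduces its subgroups as optional: "Summaries of study outcomes may be repeated focusing alternatively on but not limited to the following subgroups of interest", subject to sample size. One entry reads "Site of metastasis: Visceral, Non-visceral, Bone only".

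SAP 5.1 defines the three terms at the index date:

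- **Visceral:** at least one site on a visceral list, with the remark "Other metastasis sites, including bone or non-visceral metastasis, may be present".
- **Non-visceral:** "Metastasis at one or more of the following sites: bone, brain, skin, chest wall, contralateral breast, or distant lymph nodes". No exclusion follows.
- **Bone only:** "Bone metastasis, with no metastasis at any other identified site".

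The footnotes to Table 2a repeat these definitions; footnote e begins "Non-visceral: metastasis at one or more of the following sites: bone, brain, skin, chest wall". Neither document gives a hierarchy or a rule for a patient who meets two definitions. At the end of the figure list in Appendix 1, the SAP adds: "Additional figures will be generated for designated subgroup analyses".

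The study population is wider than metastatic disease. Protocol 9.2.1 admits A/MBC "defined as breast cancer at stage IIIB, stage IIIC, stage IV or identified as having distant metastasis", and Protocol 9.3.2 (items 9 and 10) foresees patients at Stage IIIB or IIIC on the index date and collects distant sites only where they apply.

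For Type of MBC, SAP 5.1 and Table 2a use initial stage alone: Stage 4 is De novo and Stages 0 to 3 are Recurrent. Table 2a covers All Eligible Patients, and the only other row for this variable is Missing.

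**The concern.** Three flags that work well as separate Yes/No rows are reused in SAP 4.2 as levels of a single factor. A reader of a Kaplan-Meier summary headed Non-visceral will take it to describe patients without visceral disease. As defined, it also holds patients who have visceral disease together with a bone, skin, nodal or other listed site. A reader who sees Bone only beside Non-visceral will take them as separate groups, but the first lies wholly inside the second. At stake is the correct reading of descriptive subgroup results, if they are produced.

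The Type of MBC row raises a smaller labelling question. Stage IIIB and IIIC already qualify as A/MBC. A patient first diagnosed at that stage can therefore enter the study on the initial diagnosis and be counted as Recurrent with no recurrence. Tables 2a and 2b serve Primary Objective 1a.

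**Working it through.** The plan gives no figure on this point to reproduce, so the check is logical.

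**Inputs.** The levels come from SAP 4.2, the definitions from SAP 5.1 and Table 2a footnotes d to f, and the recorded sites from Protocol 9.3.2 item 10.

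**Step 1, general count.** Write V, NV and BO for the three levels. Bone is on the NV list, so BO is a subset of NV. Hence

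n(V) + n(NV) + n(BO) = n(V or NV) + n(V and NV) + n(BO).

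The memberships exceed the patients classified by n(V and NV) + n(BO). The excess is zero only if no patient has both kinds of site and no patient is bone-only.

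**Step 2, five illustrative patients.**

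| Sites at index | V | NV | BO | Memberships | Exclusive level |
|---|---|---|---|---|---|
| bone | 0 | 1 | 1 | 2 | Bone only |
| liver, bone | 1 | 1 | 0 | 2 | Visceral |
| liver | 1 | 0 | 0 | 1 | Visceral |
| skin | 0 | 1 | 0 | 1 | Other non-visceral |
| none | 0 | 0 | 0 | 0 | outside the subgroup |
| Total | 2 | 3 | 1 | 6 | |

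Four patients yield 6 memberships: 4 + 1 + 1, as the formula gives. Of the three under Non-visceral, one has liver disease and one is also under Bone only. With exclusive levels the count is 2 Visceral + 1 Bone only + 1 Other non-visceral = 4, with 1 patient reported as outside.

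**Step 3, all patterns of the named sites.** Protocol item 10 names 5 sites that fall on the visceral list (liver, lung, peritoneum, malignant pleural effusion, and pleural nodules, which I assume count as pleura) and 6 on the non-visceral list. That gives 2^11 = 2048 present/absent patterns.

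- Any visceral and any non-visceral site: (2^5 − 1) × (2^6 − 1) = 31 × 63 = 1953. Adding bone alone (NV and BO) gives 1954 patterns in two levels.
- Exactly one level: 31 visceral only + 62 non-visceral only (63 less bone alone) = 93.
- No level: 1 (no site).
- Check: 1954 + 93 + 1 = 2048.

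Under exclusive levels: Visceral 31 × 64 = 1984, Other non-visceral 62, Bone only 1, no site 1. The sum is 2048, each pattern once. These are logical patterns and say nothing about how often each occurs in patients. The check does not cover free-text Other sites.

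**Step 4, Type of MBC.** Applying the SAP rule by initial stage, I, II, IIIA, IIIB and IIIC all give Recurrent and IV gives De novo. Of the stages labelled Recurrent, IIIB and IIIC themselves meet the A/MBC definition. The label is wrong only where that initial diagnosis is also the index diagnosis. A patient who relapsed after treatment for Stage III disease is properly recurrent.

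**The case against.** The strongest reply is that SAP 4.2 never promises a partition. It speaks of repeating summaries in one subset at a time, and that does not need exclusive subsets. Hypotheses and decision rules are not applicable (SAP 3.1, 3.2), the curves are unadjusted (7.1) and no covariates enter (7.2). The Visceral definition openly allows other sites. All of this stands, and it is why the point is minor. It does not remove the labelling problem. The other 4.2 factors with stated levels have mutually exclusive ones, so readers will expect the same here. The Bone-only definition shows that the SAP writes an exclusion where it wants one. Even if Non-visceral is read as free of visceral disease, bone-only patients still count twice.

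A reader might infer more than the documents support:

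- **That the missing level for patients without distant metastasis is a defect in itself.** This is weak. A factor about the site of metastasis naturally concerns patients who have metastasis, and other 4.2 factors are not exhaustive either: race has no unknown level, ECOG no missing level, and number of sites starts at 1. The SAP need only say that such patients are outside the subgroup.
- **That the Appendix 1 sentence commits the sponsor to figures for this subgroup.** It refers to designated subgroups without naming them, so the item remains optional.
- **That the Type of MBC row is certainly wrong.** SAP 5.1 measures time to first MBC diagnosis up to the metastatic date, which suggests that MBC may have been meant to cover metastatic patients only. Table 2a heads the corresponding row A/MBC, so usage is not consistent and the intent stays open.

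**Conclusion.** The overlap holds on the text, with high confidence, and it is minor. If the site-of-metastasis summaries are run as written, the Non-visceral result would include patients with visceral metastasis, and every bone-only patient would appear under two headings.

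A reader might infer that the main results or a subgroup comparison are distorted. They are not: the overall rwPFS, OS and rwTR results do not use these levels, no comparison between levels is planned, and the Yes/No rows of Tables 2a and 2b are correct as separate flags. The documents do not allow an effect in months or in response rate to be computed, and they give no number of affected patients. I claim neither.

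The Type of MBC point is secondary and less certain. As written, the rule mislabels a patient whose index diagnosis is an initial Stage IIIB or IIIC diagnosis. A restriction to metastatic patients may have been intended but is not stated. It touches one descriptive variable in two tables and no 4.2 subgroup.

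**What to change.** Keep the Yes/No rows of Tables 2a and 2b. For the SAP 4.2 subgroup only, define exclusive levels at the index date:

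- **Visceral:** any site on the SAP visceral list, including such sites recorded under Other.
- **Bone only:** as now defined.
- **Other non-visceral:** any other documented distant site, including Other sites not on the visceral list, with no visceral site and not bone only.

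State that patients with no distant metastasis or with undocumented sites are outside this subgroup, and give their number. Free-text Other entries must be read against the visceral list before assignment.

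For Type of MBC, restrict the row to patients with Stage IV/metastatic disease at index and state that denominator under the table. A separate locally advanced category that requires the index date to equal the initial diagnosis date is not advisable. The two dates are abstracted separately, and a short staging interval would return such patients to Recurrent.

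The cost is a few lines of SAP text, small changes to derivation code and footnotes, and smaller subgroup cells in a subgroup already conditional on sample size. No new abstraction is needed: initial stage, index stage and distant sites are already collected (Protocol 9.3.2 items 3, 8 and 10).
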